6.3 TheraSphere

TheraSphere treatment is performed in the outpatient setting. Prior to initial treatment, a Technetium-99 Macroaggregated Albumin (Tc-99m MAA) scan will be performed using standard institutional practices. If there is an uncorrectable risk of flow to the gastrointestinal organs or risk of excessive shunting to the lungs, TheraSphere treatment will not be administered and the patient will receive alternative or no treatment as previously defined in the treatment plan

Following treatment, patients will remain at the hospital under medical observation until the physician determines that they can safely be discharged to home (usually 2-6 hours). All patients will be evaluated post-treatment to assess clinical experience and adverse experiences.

Patients will have 1-2 outpatient visits for pre-treatment evaluation to determine initial eligibility to receive TheraSphere, followed by a treatment visit for outpatient delivery of TheraSphere,.

Catheters will be placed in the hepatic artery in the angiography suites. No scheduled hospitalizations will be required, unless the physician determines that the patient should be admitted following treatment for management of a complication or adverse experience.

Pre-Therasphere Evaluation

Pre-treatment evaluation will include the initial screening by history, physical examination, laboratory and diagnostic studies (hepatic angiography and Tc-MAA Scan). A treatment plan will be developed, dosage will be calculated, and the initial TheraSphere activity vial will be ordered from the manufacturer (Nordion).

Diagnostic Imaging Studies

Contrast enhanced Computed Tomography Scanning of the Abdomen/Liver or Magnetic Resonance Imaging of the Abdomen/Liver

Technetium-99 Macroaggregated Albumin (Tc-99m MAA) Scan.

CT or MR scanning of the liver will be performed and the images used to calculate the appropriate liver volume for TheraSphere dose determination. Reasonable attempts will be made to use the same imaging modality as that used for pre-treatment for all subsequent evaluations of the patient related to dose determination.

The dose is calculated as described below (Section 7.3.3.4), using the appropriate reference liver volume and mass. Dosimetric techniques for TheraSphere are discussed in detail in the peer-reviewed literature.

The imaging scan is used to document the location and size of the hepatic lesion(s) and vascular anatomy where possible.

Prior to first TheraSphere treatment a Tc-99m MAA scan will be performed to obtain a preliminary assessment of hepatic infusion and any potential extrahepatic shunting or gastrointestinal flow. Lung Shunt Fraction will be determined as the ratio of total lung counts divided by total hepatic plus lung counts.

If gastrointestinal flow is detected, steps will be undertaken (embolization, change in catheter position) to correct this flow, prior to TheraSphere administration. If gastrointestinal flow cannot be corrected using established angiographic techniques, the patient may not receive TheraSphere treatment.

Only after extrahepatic exposure has been evaluated and the patient deemed to meet eligibility criteria, may TheraSphere be administered.

To be eligible to receive TheraSphere treatment, the potential absorbed dose to the lungs must be < 30 Gy (< 16.5mCi of injected activity) per treatment. Any uncorrected detectable gastrointestinal flow is a contraindication to TheraSphere treatment.

Treatment Planning

The principal investigator with the Authorized User will formulate the initial treatment plan, indicating the number and sequence of planned TheraSphere treatments. The clinician will assure that the patient understands the two-stage screening process that is necessary for this treatment procedure. The physician and patient will discuss and agree on a contingency treatment plan, including the option of no treatment, in the event that the patient is found ineligible to receive TheraSphere after catheter placement. The Treatment Plan may be modified following initial treatment, based on clinical experience and patient response to treatment.

TheraSphere Dose Calculation

The target dose of TheraSphere used is 80 – 150 Gy. Depending on the timing of the product order relative to the TheraSphere production schedule, and the treatment date proposed for the patient, it may be necessary to allow TheraSphere to physically decay to the appropriate targeted activity before injection.

The amount of radioactivity required to deliver the dose to the selected liver target is calculated using the following formula:

$$\text{Activity Required (GBq)} = \frac{[\text{Desired Dose (Gy)}][\text{Mass of Selected Liver Target (kg)}]}{50}$$

In nearly all cases more than 95% of the glass microspheres are delivered. Calculation of the liver dose (Gy) delivered after injection uses the following formula:

$$\text{Dose (Gy)} = \frac{50 [\text{Injected Activity (GBq)}][1-F][1-R]}{\text{Mass of Selected Liver Target (kg)}}$$

Where F is the fraction of injected activity deposited into the lungs as measured by Tc-99m MAA and R is the calculated residual.

TheraSphere Ordering

The TheraSphere order will be placed by the Authorized User or designated colleague. Upon completion of the pre-treatment screening evaluation, treatment plan and dose calculation, a TheraSphere order form will be sent to TheraSphere Customer Support, either by E-mail to [contact] or by fax to [name]). The deadline for order is the Tuesday **prior** to calibration date to permit inclusion of your order in the weekly dispensing cycle.

TheraSphere is viable for therapeutic use for up to 12 days after the calibration date. TheraSphere will be shipped by MDS Nordion to ensure that TheraSphere is on-site by the proposed treatment date. To meet the desired absorbed dose to the patient's liver, the clinician must schedule the patient's TheraSphere treatment visit to occur within 12 days of the calibration date, and take into consideration the appropriate physical decay of the dose activity.

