2.2 Global Regulatory Status of Therasphere

TheraSphere received a Humanitarian Device Exemption (HDE) from the United States Food and Drug Administration (FDA) in 1999 (HDE H980006) and is currently approved for use in radiation treatment or as a neoadjuvant to surgery or transplantation in patients with

unresectable hepatocellular carcinoma (HCC) who can have placement of appropriately positioned hepatic arterial catheters. The device is also indicated for HCC patients with partial or branch portal vein thrombosis/occlusion, when clinical evaluation warrants the treatment. The current US package insert is provided in Appendix 1a.

TheraSphere is approved for use in Europe for the treatment of hepatic neoplasia. TheraSphere is approved in Canada for the treatment of hepatic neoplasia in patients who have appropriately positioned arterial catheters. In addition, TheraSphere is available in Russia, India, South Africa and Kuwait for the treatment of hepatic neoplasia.

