11.1 Ethical and legal conduct of the study

The procedures set out in this protocol, pertaining to the conduct, evaluation, and documentation of this study, are designed to ensure that the investigator abide by Good Clinical Practice (GCP) guidelines and under the guiding principles detailed in the Declaration of Helsinki. The study will also be carried out in keeping with applicable local law(s) and regulation(s).

Documented approval from appropriate IEC(s)/IRBs will be obtained for all participating centers before start of the study, according to GCP, local laws, regulations and organizations. When necessary, an extension, amendment or renewal of the EC/IRB approval must be obtained and also forwarded to Bayer.

Strict adherence to all specifications laid down in this protocol is required for all aspects of study conduct; the investigator may not modify or alter the procedures described in this protocol.

Modifications to the study protocol will not be implemented by the investigator without discussion and agreement by Bayer. However, the investigator may implement a deviation from, or a change of, the protocol to eliminate an immediate hazard(s) to the trial subjects without prior IEC/IRB/Bayer approval/favorable opinion. As soon as possible, the implemented deviation or change, the reasons for it and if appropriate the proposed protocol amendment should be submitted to the IEC/IRB/head of medical institution. Any deviations from the protocol must be explained and documented by the investigator.

The Principal Investigator is responsible for the conduct of the clinical trial at the site in accordance with Title 21 of the Code of Federal Regulations and/or the Declaration of Helsinki. The Principal Investigator is responsible for personally overseeing the treatment of all study patients. The Principal Investigator must assure that all study site personnel, including sub-investigators and other study staff members, adhere to the study protocol and all FDA/GCP/NCI regulations and guidelines regarding clinical trials both during and after study completion.

The Principal Investigator at each institution or site will be responsible for assuring that all the required data will be collected and properly documented.

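### Section 6.3 labels the activity equivalent of the 30 Gy lung limit as injected activity; 16.5 mCi fits only as activity reaching the lungs

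*Combined protocol and SAP*

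**What the plan says.** Section 6.3 has a Tc-99m MAA scan done before TheraSphere. It defines the shunt measurement: "Lung Shunt Fraction will be determined as the ratio of total lung counts divided by total hepatic plus lung counts". Shortly afterwards it sets the condition for treatment: "the potential absorbed dose to the lungs must be < 30 Gy (< 16.5mCi of injected activity) per treatment". The opening of the section gives the consequence where there is a "risk of excessive shunting to the lungs, TheraSphere treatment will not be administered".

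Under the dose calculation heading of the same section, the plan states "The target dose of TheraSphere used is 80 – 150 Gy" and computes the activity to order as desired dose times target liver mass, divided by 50. A second formula gives the delivered liver dose as 50 times injected activity, times (1 − F), times (1 − R), divided by target mass. It is followed by the definition "Where F is the fraction of injected activity deposited into the lungs as measured by Tc-99m MAA and R is the calculated residual".

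The visible text gives no lung-dose formula and no lung mass, and it sets no limit on F times activity. Section 6.3 refers to a Section 7.3.3.4 for the dose calculation, but the document has no such section. Section 2.2 says "The current US package insert is provided in Appendix 1a"; that appendix is not in the text available here.

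**The concern.** The delivered-dose formula fixes the meaning of injected activity. It is everything given, from which the lung fraction F and the residual R are then removed. A limit on that quantity is not a limit on lung dose, because the same injected activity gives a small or a large lung dose depending on F. The protocol measures F just before stating the limit, but the parenthesis does not use it.

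The sentence is a treatment-eligibility threshold, and Section 11.1 says "Strict adherence to all specifications laid down in this protocol is required for all aspects of study conduct". If the parenthesis were applied as printed, a patient who meets the 30 Gy limit could be refused Y-90. If it were ignored, treating any target above a few hundred grams would be a deviation on paper. Section 1.1 reports 20 patients accrued and Section 8.1 sets a maximum of 40, so the sentence can still affect up to 20 patients.

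**Working it through.** **Inputs from Section 6.3:** lung limit 30 Gy; stated equivalent 16.5 mCi; constant 50 Gy per GBq/kg; target dose 80–150 Gy. **Unit conversion:** 1 mCi = 0.037 GBq. **Assumed, because the documents give no values:** lung mass 0.8–1.2 kg, shunt fraction F 5–20%, target liver mass 0.5–1.5 kg.

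**1. Can the stated equivalence be reproduced?** Not from the documents alone, because lung mass is missing.
- 16.5 × 0.037 = 0.6105 GBq.
- As activity in the lungs, the dose is 50 × 0.6105 / lung mass: 38.2 Gy at 0.8 kg, 30.5 Gy at 1.0 kg, 25.4 Gy at 1.2 kg.
- It is exactly 30 Gy at 50 × 0.6105 / 30 = 1.0175 kg.
- Conversely, 30 Gy corresponds to 30 × lung mass / 50: 0.48 GBq (13.0 mCi) at 0.8 kg, 0.60 GBq (16.2 mCi) at 1.0 kg, 0.72 GBq (19.5 mCi) at 1.2 kg.

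So 16.5 mCi is a sensible figure for activity reaching about 1 kg of lung.

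**2. The same figure as injected activity.** Lung dose = 50 × 0.6105 × F / lung mass.

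| F | 0.8 kg | 1.02 kg | 1.2 kg |
|---|---|---|---|
| 5% | 1.9 Gy | 1.5 Gy | 1.3 Gy |
| 10% | 3.8 Gy | 3.0 Gy | 2.5 Gy |
| 20% | 7.6 Gy | 6.0 Gy | 5.1 Gy |

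At a lung mass of 1.02 kg, 16.5 mCi injected gives 30 Gy only if F = 1.

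**3. Literal cap against the planning formula.** Largest target mass = 0.6105 × 50 / dose.
- 80 Gy: 0.382 kg.
- 150 Gy: 0.204 kg.

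**4. Assumed target sizes.** Planned activity = dose × mass / 50. The last column is the F at which a limit of 0.6105 GBq on F × injected activity would bind, which is 0.6105 / planned activity.

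| Target | Planned activity, 80–150 Gy | Multiple of literal cap | F at which the limit binds |
|---|---|---|---|
| 0.5 kg | 0.8–1.5 GBq | 1.3–2.5 | 76–41% |
| 1.0 kg | 1.6–3.0 GBq | 2.6–4.9 | 38–20% |
| 1.5 kg | 2.4–4.5 GBq | 3.9–7.4 | 25–14% |

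At the literal cap a 1.0 kg target could receive at most 50 × 0.6105 / 1.0 = 30.5 Gy before shunt and residual, against a target of 80–150 Gy.

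**The case against.** The best defence is that the literal reading is not the natural one. The subject of the sentence is lung dose, and the parenthesis glosses it, so the phrase could mean the part of the injected activity that reaches the lungs. The context supports this. The shunt fraction is measured just beforehand, Y-90 is withheld for excessive shunting and not for total activity, and a cap on total activity would make the shunt irrelevant to lung eligibility. The smallest vial in Section 2.1 is 3 GBq, 4.9 times the literal cap. A trained user would very likely apply F times activity. All of this stands as evidence of intent. It does not make the label right: the formula in the same section uses the term for the total, and nothing visible corrects the sentence.

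The package insert may give a lung mass. That is a fair caution about which mCi value is right, but an appendix supplying a mass would not repair the protocol's own sentence.

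Three stronger inferences are tempting, and the documents do not support them.
- **That patients are at risk of lung overdose.** The error works the other way: step 2 gives 1.3–7.6 Gy at the literal cap, and the 30 Gy criterion itself is sound.
- **That patients have been wrongly refused Y-90.** Section 1.1 describes no exclusion or breach linked to this line for the 20 patients accrued. Its silence proves nothing either way.
- **That the cap would stop all treatment.** The documents give no target masses, and Section 6.4 describes selective infusion, so targets below 0.38 kg cannot be ruled out. A 3 GBq vial with a 64.2 h half-life decays to 0.61 GBq in 64.2 × ln(3 / 0.6105) / ln 2 ≈ 147 h, about 6 days, within the 12-day window.

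**Conclusion.** Wrong as written; minor. The number is about right for activity deposited in the lungs and wrong for the quantity it is attached to.

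The 0.38 kg and 0.20 kg ceilings need only the protocol's constant, its target doses and the unit conversion. The match to 30 Gy rests on an assumed lung mass near 1 kg, and the multiples in step 4 rest on assumed target sizes. Lung-deposited activity is the probable intent, so the practical effect depends on how literally the line is applied to the patients still to be enrolled. No endpoint, analysis or stopping rule is affected.

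**What to change.** Make < 30 Gy the governing criterion in Section 6.3 and state how it is computed: lung dose (Gy) = 50 × injected activity (GBq) × F / lung mass (kg), with the lung mass the sponsor uses. Then do one of two things:
- delete the mCi parenthesis; or
- replace it with a limit on F × injected activity, at the mCi value that gives 30 Gy for the stated lung mass: 13.0 at 0.8 kg, 16.2 at 1.0 kg, 16.5 only at about 1.02 kg, 19.5 at 1.2 kg.

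Inserting F while keeping 16.5 mCi regardless of lung mass would not be enough. At 1.0 kg that limit allows 30.5 Gy, just over the criterion.

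The cost is one parenthesis and one formula. F and injected activity are already obtained, so no new data are needed. The only new commitment is a stated lung mass. The planning formula and the 80–150 Gy target stay as they are.

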6.4 Procedures on Day of Treatment

Treatment with TheraSphere may be performed in the outpatient setting. The following sections describe the procedures performed on day of treatment.

Catheter Placement and TheraSphere Infusion

The goals of percutaneous catheter placement for TheraSphere administration are: first, to limit the perfusion to the normal liver, and, second, to deliver TheraSphere as specified in the treatment plan.

On the day of treatment, TheraSphere is administered via infusion under imaging guidance through an hepatic arterial catheter appropriately positioned in the arterial anatomy to permit selective infusion of TheraSphere into the target tissue selected for treatment. The interventional radiologist will perform this procedure. The patency of the catheter will be maintained using standard techniques. Administration of TheraSphere

Regardless of catheter size or infusion pressure used, the flow of the microspheres will mimic the flow dynamics of the vessel being infused.

The TheraSphere administration procedure is described in the TheraSphere package insert and in peer-reviewed literature. Patient Management

Following treatment, the patient will remain under observation consistent with standard care guidelines for aftercare procedures involving arterial catheterization. The patient will be sent home when the physician determines that the patient is stable and that there is no risk of bleeding from the access site. At the time of discharge, patients will be instructed per institutional guidelines regarding after-care including instructions if they develop a problem.

Because there may be small unrecognized arterial vessels connecting to the gastrointestinal system, prophylactic anti-ulcer medication is recommended at discharge. Gastric coating agents and tapering 5 day steroid dose pack (to reduce fatigue unless contraindicated) may also be given.

Special radiation isolation procedures are not necessary following TheraSphere treatment.

6.5 Radiation Safety in the Post-Treatment Period

If a patient receives a liver transplant or dies in the immediate period following treatment with TheraSphere, radiation safety guidelines for handling of the body and/or body tissues should be followed, as dictated by institutional radiation safety policy.

There are no federal regulations that clearly address the radiation safety issues related to handling of liver tissue following TheraSphere treatment. The surgeon and oncologist will consider the risks and benefits of the clinical circumstances and relevant institutional policy, before determining whether, and when, it is safe to proceed with procedures that require direct handling of TheraSphere-treated liver tissue in the immediate post-treatment period.

Most patients have surface dose rates $<20\mu\text{Sv/h}$ at 30 days following treatment. Generally a patient skin surface dose rate of $<20\mu\text{Sv/h}$ does not require special handling (such as lead gloves, special instruments and extremity radiation monitors) by the surgeon during the operation. Notify radiation safety personnel for transportation and storage of the explanted tissue.

Very small amounts of longer-acting radioactive by-products have been noted. These by-products are well within known toxicity levels but may present some post-mortem tissue handling issues. Some regulatory jurisdictions are developing policies regarding handling of long lived by-products post mortem, specifically in regards to cremation; relevant institutional policy should be considered.

Travel documentation may be offered to patients who need to cross international borders, as the long lived activity may be detectable with the sensitive equipment at some facilities.

6.6 Device Dosages

The target dose of TheraSphere used is 80 – 150 Gy. Standard radiation safety techniques should be used.

Glass microspheres are typically 20-30 micrometers (μm) in diameter, or about 3-4 times the size of a red blood cell. In a report of 420 independent pre- and post treatment angiographic observations, macroscopic embolization of the hepatic arteries was not observed indicating hepatic perfusion is maintained.

7. Procedures and variables

7.1 Schedule of procedures

7.1.1 Tabulated overview

CLINICAL AND LABORATORY EVALUATIONS [Table 7]

	Pre-Study [@]	Cycle 1, Day 1	Cycle 2 & Subsequent Cycles Day 1 ^f , #	End of Cycle 3, 5, & every 2 cycles [#]	End of Treatment #	Post Treatment Follow-up
Informed consent	X					
Demographics	X					
Medical History	X		X		X	
Concurrent Medications*	X		X		X	
Physical Exam	X		X		X	
Height	X					
Weight	X	X	X		X	
Vital Signs (Includes SBP/DBP)	X	X	X		X	
Urinalysis w/urine protein	X			X	X	
Performance status	X		X		X	
Hepatitis profile ⁱ	X					
PT/PTT/INR ^a	X		X		X	
CBC with differential, platelets	X		X		X	
Serum chemistry ^b	X		X		X	
Liver function tests ^c	X		X		X	
ECG	X					
β-HCG (women of child-bearing potential)	X					
AFP ^d	X		X		X	
CT/MRI abdomen and pelvis Tumor Assessment ^e	X			X	X	
TheraSphere		Therapy 4 (+/- 1) weeks after starting Sorafenib				
Sorafenib		Daily continuous 400 mg, orally, twice a day				
Adverse events	X ^g		X		X	
Survival						X ^h
Plasma samples ^j	X	X	Cycles 2, 3, day of Y-90		X	

[@] Pre-study evaluations except for imaging studies, Hepatitis profile must be obtained within 7 days prior to first day of treatment. Baseline imaging studies may be obtained up to 28 days prior to first day of treatment. Hepatitis profile must be obtained within 3 months prior to first day of treatment

[#] Evaluations may be obtained within (+/-) 72 hours of starting a new cycle, except for imaging studies which may be obtained within 7 days prior to starting a new cycle.

*All medications, including prescription and over-the-counter, vitamins, supplements and

"herbal" preparations must be disclosed by the patient and recorded. Patients will be instructed to check with study staff before taking any new prescription or over-the-counter medication(s), vitamins, supplements and/or "herbal" preparations

^a Weekly monitoring of INR for patients on warfarin, however, these patients will be switched to enoxaparin if possible.

^b Includes BUN, creatinine, sodium, potassium, carbon dioxide, chloride, phosphorus, magnesium, calcium, protein, glucose.

^c Includes AST (SGOT), ALT (SGPT); total, direct and indirect bilirubin; LDH, alkaline phosphatase, albumin; (GGT will be run for alkaline phosphatase that is ≥ 150 IU/L. GGT will be run with the first elevation of alkaline phosphatase and will not be repeated for future alkaline phosphatase elevations)

^d Alpha-feto protein.

^e CT will be the radiographic study of choice for baseline (CT of the chest is included at baseline) and re-staging evaluations (CT of the chest may be included if needed in re-staging); MRI may be substituted at any time in the course of the study as clinically warranted (eg iodine dye intolerance, elevated creatinine, tumor not clearly depicted on CT)

^f Treatment may continue after Course 2, including the same study assessment schedule, until one of the criteria for treatment discontinuation applies.

^g Patients who have an ongoing Grade ≥ 3 or serious adverse event that is at least possibly related to treatment will be contacted by the investigator or designee every week until the event is resolved or determined to be irreversible.

^h Every 3 months after discontinuation of treatment

ⁱ Hepatitis profile to include the following tests: hepatitis B virus surface antigen (HBSAG), hepatitis B virus core antibody (HBCAB), and hepatitis C virus antibody (HCVAB).

^j Samples Collection: Blood samples will be collected at the time of patients' scheduled visits as follows:Procedure for samples collection:

GI Medical oncology Research Staff will inform blood draw station to collect an extra set of blood sample (3 ml purple top tube with EDTA) for the purpose of the study, on the day of the patient's initial visit and per scheduled samples collection per protocol. at the GI Medical Oncology clinic visits. Collection times will correspond to those at which subjects are already having blood drawn for other purposes. Maximum blood draws would be 6 total(1) Screening; (2) Cycle 1/Day 1; (3) Cycle 2/Day 1; (4) Cycle 3/Day 1; (5) Pre-Yttrium-90, on the same day; and (6) End of Treatment. Once blood is collected, GI Medical Oncology research personnel will pick it up and deliver it to the laboratory of [name] and [name] for processing in batch and storage in freezer in -80 F. Processing will involve isolating plasma samples. **Cycle 1/Day 1** sample will be collected only if **Screening** sample was collected more than 7 days prior. **Pre-Yttrium-90** sample will be collected only if **Cycle 2/day 1** sample was collected more than 7 days prior. And vice versa, **Cycle 2/Day 1** sample will be collected if **Pre-Yttrium-90** sample was collected more than 7 days prior.

Samples will each be labeled according to the sample label listed below.

Sample label or per Z code labeling

Protocol #	sample
Subject Accession # -	
Date/Time prepared -	

